**Aim 2** will address the degree to which people with disabilities experience healthcare disparities. The comparators will be the outcome here and ADL/IADL stages will be the main exposure. We will model each trichotomously expressed comparator through multinomial logistic regression. We will report adjusted relative risk ratios (RRRs) and their 95% confidence intervals (CIs) for the ADL and IADL stages (stage I as reference). For each continuously expressed comparator, we will report sample weighted estimates for the ADL and IADL stages (stage I as reference) obtained through linear regression.

**Aim 3** will determine if people who experience better access and higher quality healthcare and who rate their PCPs highly on technical skills, inter-personal manner, and the provision of sufficient information to understand their health condition(s) will be less likely to experience a negative transition outcome. The 5-state transition outcome will be modeled by multinomial logistic regression models with no change in function as reference. We will report RRRs and their 95% CIs. In the multinomial logistic regression, the relative risk of improvement in function, decline in function, institutionalization, or death will be defined as the probability of improvement in function, decline in function, institutionalization, or death divided by the probability of remaining at the same ADL stage.

Each of the 5 comparators will be modeled individually after considering other covariates. They will also be entered into one model to determine the relative independent effects of each after considering the other exposures.

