**Aim 4** While models for aims 2 and 3 will be etiological and explanatory, the policy simulations will be predictive. We will simulate the maximum benefit of healthcare programs or policies aimed at improving each comparator, i.e., coordination and quality of care, increasing access, PCP technical skills, PCP interpersonal skills, and the quality of information provided by PCPs on likelihood of functional improvement, functional decline, institutionalization, or death over 1, 2, and 3 years. Taking the scenario of increased access as example, the simulation will: estimate the effect of poor access to care according to the transition outcome using  $\beta$ -coefficients from a multinomial regression similar to those proposed in Aims 2 and 3, i.e., we will use coefficients to predict status according to the multiple outcome states of "improved in function," "deteriorated in function," "institutionalized," and "died" by 1-, 2- and 3-year follow-up compared to "remained at the same ADL stage," given the new optimized access comparator, while holding baseline ADL stage and all other variables constant at the individual-levels. This will allow creation of new population prevalence estimates for each of the outcome states assuming optimal access. Comparison of these predicted/adjusted values and their associated confidence intervals will show the relative potential of policies targeted to improve the access comparator (when compared to any other policy change scenario) included in the simulation. Simulations will be performed for the 1-, 2- and 3-year time frames and for ADL and IADL stage transitions. This will produce a table showing the regression-based, predicted effects of optimizing alternative comparators on population status. These simulations will help frame the results of our study according to the "comparative effectiveness" of alternative policy instruments targeted to the 5 quality comparators. These findings will be triangulated with thematic materials extracted from the stakeholder groups (see above).

PRINCIPAL INVESTIGATOR (LAST, FIRST, MIDDLE): [name]

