**Quantitative: Overview and General Approach to Multivariable Estimation:** Our specific aims focus on empirically quantifying disparities in the quality of health and PCP care as perceived by PWD compared to PWOD and the impact of any disparities identified on transition outcomes. Taking advantage of the large nationally representative contemporary cohort of Medicare beneficiaries enrolled over a decade in the MCBS, quantitative methods will begin by

PRINCIPAL INVESTIGATOR (LAST, FIRST, MIDDLE): [name]

exploring the associations of all covariates to ADL and IADL stage transitions over 1, 2- and 3-year periods. A series of multivariable regressions will be implemented in Aims 2, 3, and 4 to provide a comprehensive perspective on disparities and the factors influencing transitions. After quantifying the net contribution (if any) of each comparator to outcome transitions, we will then use parameter estimates generated by these analyses in the Aim 4 simulation study. The goal will be to simulate the maximum effect of alternative programs intended to improve access to care, quality of care, and the technical and other qualities of PCPs on the wellbeing of the US Medicare population.

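### Aim 4 plans no confidence interval for the difference between policy scenarios; reading the separate intervals is conservative and may hide real differences

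*Combined protocol and SAP*

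**What the plan says.** Under Data Analysis, Aim 4 takes a multinomial regression, sets one comparator to its optimized value, and predicts each person's outcome while "holding baseline ADL stage and all other variables constant at the individual-levels". The example given is access, and the predictions yield "new population prevalence estimates for each of the outcome states assuming optimal access". The step from scenarios to conclusions is one sentence: "Comparison of these predicted/adjusted values and their associated confidence intervals will show the relative potential of policies". The comparison is made against any of the other scenarios simulated, and it is repeated for 1, 2 and 3 years and for ADL and IADL stages. The results are meant to express the comparative effectiveness of policies aimed at the five comparators.

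The source model is described only as "coefficients from a multinomial regression similar to those proposed in Aims 2 and 3". Aim 3 offers two candidates: "Each of the 5 comparators will be modeled individually after considering other covariates" and "They will also be entered into one model to determine the relative independent effects of each after considering the other exposures". The quantitative overview in the Project Plan and Timeline says "we will then use parameter estimates generated by these analyses in the Aim 4 simulation study", without saying which of the two is meant.

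Neither place defines a between-scenario difference or gives it an interval. The general two-sided 5% rule is not tied to any Aim 4 contrast, and the power calculation covers Aims 2 and 3 only.

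**The concern.** The Aim 4 question is comparative: which of five levers would do most for function, institutionalization and survival. The natural estimand is a difference between two standardized prevalences. An interval around each prevalence describes how well that one prevalence is known, which is a different matter.

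If readers judge the policies by whether the separate intervals overlap, they apply a stricter standard than the 5% level used elsewhere in the plan. Simulation results are to be shown to stakeholder groups as scenarios and used to shape recommendations, so overlap could easily be taken to mean no difference. The risk is greater in small strata. The Year 3 deliverables promise results at each disability stage, and Table 5 has ADL stage IV at 185 of 12,058, or roughly 600 of the expected 40,000. Separate intervals there will be wide.

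**Working it through.** Aim 4 states no interval width, power or sample size of its own, so there is no figure to reproduce. The check is algebra, one worked example and a simulation.

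**Algebra.** Let SE1 and SE2 be the standard errors of two scenario prevalences and r their correlation.
- Non-overlap of two 95% intervals needs a gap above 1.96 × (SE1 + SE2).
- A direct contrast needs a gap above 1.96 × √(SE1² + SE2² − 2·r·SE1·SE2).
- The first is never smaller than the second. With equal SEs the ratio is 2/√(2(1 − r)).

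A contrast with 80% power has a true difference of 1.96 + 0.84 = 2.80 standard errors. The power of non-overlap is then P(Z > 1.96 × ratio − 2.80).
- r = 0: ratio 1.41, power 51%.
- r = 0.5: ratio 2.00, power 13%.
- r = 0.7: ratio 2.58, power about 1%.

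**Worked example** (assumed coefficients; a logistic stand-in for one outcome equation; 40,000 people; comparators correlated 0.3; joint model; everyone moved to best). SE1 = 0.00335, SE2 = 0.00340, SE of the difference = 0.00445.
- Ratio: (0.00335 + 0.00340)/0.00445 = 1.52.
- Threshold on the contrast scale: 1.96 × 1.52 = about 2.97, an effective two-sided level of about 0.003.
- Power: P(Z > 2.97 − 2.80) = about 43%.
- Implied correlation: (0.00335² + 0.00340² − 0.00445²)/(2 × 0.00335 × 0.00340) = 0.13.
- At r = 0 the same SEs give 0.00675/0.00477 = 1.41. So most of the excess over 1 (0.41 of 0.52) comes from adding the margins, and only about 0.10 from correlation.

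**Simulation.** From the documents: five outcome states, five trichotomous comparators, 40,000 people, and prevalences standardized over the same individuals. Assumed: comparator split 25/50/25; yearly rates of about 10% improvement, 11% deterioration, 1.8% institutionalization and 5% death; latent correlation between comparators of 0.2, 0.5 and 0.7; no design effect. Ranges below pool deterioration and death over the three correlations, with everyone moved to the best level.
- Joint model: gap needed for non-overlap 0.85–1.56 percentage points, for the contrast 0.55–1.14; ratio 1.4–1.5; power of non-overlap 41–54% where the contrast has 80%. Here r was only about −0.05 to 0.16.
- Separate models: 0.77–1.15 against 0.36–0.67 points; ratio 1.7–2.2; power 7–31%.

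As one line from the joint model (latent correlation 0.7, deterioration): SEs 0.00400 and 0.00398, SE of the difference 0.00579. Non-overlap needs 1.96 × 0.00798 = 1.56 points; the contrast needs 1.96 × 0.00579 = about 1.14 points.

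**The case against.** The strongest reply is that the plan contains no overlap rule. It says the values and intervals will show relative potential; it does not say that overlapping intervals mean equal policies. That stands. The power figures describe a reading the text invites, not a test it specifies.

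The error is also conservative: it creates no false policy differences. Large differences would still separate, and ordering policies by point estimate gives the same order with or without the contrasts. All of this stands and limits the point.

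Aim 4 also promises a table of predicted effects of optimizing each comparator. An effect of optimizing is naturally a change from current status, so a contrast with the status quo may already be intended, with only its interval undescribed. The absence of a between-policy interval is the firmer finding.

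Three stronger readings are tempting and not supported:
- A reader might infer that the loss arises because all scenarios share people and coefficients. Shared coefficients hold only under the joint model, which Aim 4 does not commit to. The people may also differ, because PCP comparators exist for only about 90% of patients. In the joint, everyone-to-best case the correlation is small anyway.
- A reader might infer a factor of about 3. That arises when only the worst category is removed. Aim 4 speaks of maximum benefit and optimal access, which points to moving everyone to the best level.
- A reader might infer that real differences will be missed. They may be.

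**Conclusion.** The concern holds in limited form. Aim 4 sets separate scenario intervals side by side and plans none for the differences, so the uncertainty reported does not match the comparative question. Under a joint model with everyone at the best level, judging by non-overlap needs a gap about 1.4 to 1.5 times that of a direct contrast, with power of about 41 to 54% in place of 80%. With separate models the factor is about 1.7 to 2.2.

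The direction follows from algebra and needs no assumption. The sizes rest on assumed coefficients, outcome rates and comparator correlations, and on no design effect. A design effect common to all scenarios would widen the gaps in percentage points but leave the ratios unchanged. The ranking by point estimate is not in question. This should be changed; it does not invalidate Aim 4.

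**What to change.** Add to Aim 4:
- Which model supplies the coefficients, joint or separate. The choice changes the estimand, because the joint model gives mutually adjusted effects.
- What shift optimized means for each comparator, including how people without a PCP are handled in the PCP scenarios.
- For each pair of policies, and each policy against the status quo, the difference in standardized prevalence with a design-based 95% interval on that difference. Use the delta method on the joint model, or replicate weights or a survey bootstrap that refits all models in each replicate so that the covariance is kept. Compute the difference within each of the five imputed datasets and then combine.
- That statements about relative policy potential rest on these intervals.

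The cost is modest: no new data, a short text change, and extra code, more of it if separate models are kept. The main drawback is volume. Ten pairs × four non-reference outcomes × three horizons × two staging systems gives 240 pairwise intervals, and five status-quo contrasts on the same grid add 5 × 4 × 3 × 2 = 120. Label them descriptive, or name a few key outcomes and horizons in advance.

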#### Data Analysis

Complex survey design: The MCBS uses a multi-stage clustering sample with unequal sampling probabilities. We will take into account the complex design by using appropriate survey commands in Stata to calculate the correct point estimates and their variances. Specifically, the set of longitudinal weights (RIC X2) allowing analysis of data trends over a two year period and a second set of longitudinal weights (RIC X3) will be applied to two- and three-year outcomes.

Proxies: Proxy responses will be included in all models. About 9.8% of MCBS baseline interviews were conducted by proxies and our previous work indicates that exclusion of proxy responses results in underestimates of disability prevalence. Recognizing this may explain proxy differences we will explore replacing proxy status with reason for proxy use.

Missing data and attrition: See Avoidance of Bias below.

General approach to analysis: Each Aim will describe the sample of Medicare beneficiaries with weighted uni-variable summary statistics appropriate to the distributional characteristics of the variables of interest and bi-variable associations with outcomes. Because of concerns that some variables may be intermediate on causal pathways, to understand associations, we will build etiological models hierarchically. All will control for baseline age, gender, race, ADL or

PRINCIPAL INVESTIGATOR (LAST, FIRST, MIDDLE): [name]

IADL stage, and proxy status. Health conditions and living circumstances will be added sequentially, selected according to associations with functional change, institutionalization, or mortality or according to emergent themes from stakeholder groups. The Goodness-of-Fit (GOF), Deviance and Pearson GOF Statistic, ROC curve, and r-square values as appropriate to each regression will be reported to document model fit of the multinomial regressions. Stata 11.0 (Stata Corp, College Station, Texas) will be used for all analyses (except for multiple imputation as noted below). A 2-sided  $p<.05$  will be used for all final tests of significance.

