The **Patient-Informed Surveillance Tool** will be developed in three steps using an approach we applied recently. (1) assess the quality of candidate predictors through the combined input of stakeholder and researcher recommendations with demonstrated bi-variable associations  $p < .20$ ; (2) beginning with a regression containing all candidate covariates, estimate a parsimonious model by using backward selection to remove all candidate variables at  $p > .05$ ; (3) develop a simply applied point-scoring system from the estimates associated with each variable in the final model by dividing each significant  $\beta$ -coefficient by the lowest significant  $\beta$ -coefficient and rounding to the nearest integer. A value of "0" will be assigned to non-significant  $\beta$ -coefficients. Depending on demonstrated affect modification, working-aged and elderly beneficiaries might be included in separate Tools. The final set of **Patient-Informed Surveillance Tools** will group sub-populations by outcome expectation as determined by perceptions according to each comparator adjusted for ADL or IADL stage, living circumstances (i.e., family members who might provide care, home accessibility, etc.), diagnoses, socioeconomic status (i.e., income, education, etc.), comparator status, and other covariates. The final selection of variables in the Tools will be informed by stakeholder input (see above) as well as statistical findings.

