#### Sample size

We did power calculation for Aims 2 and 3. Here, we focus on the association between ADL stage and the first comparator, care coordination and quality, in Aim 2, and that between the first comparator and transition in Aim 3.

First, we show the detectable RRRs for associations between ADL stages and the first comparator. Using our preliminary data in Table 2 which included three panels, we assume the distribution of the ADL stages will be similar across 10 years for which we will request the data for the project. After trichotomizing the first comparator, we obtained the proportion for the three categories (1, 2, and 3 from dissatisfied to satisfied) for stage I. They are 13.32%, 60.19%, and 26.49%.

Relative risk of being dissatisfied is defined as the probability of being dissatisfied divided by the probability of being neither dissatisfied nor satisfied. The detectable RRRs comparing other stages to stage I are shown in Table 3. With 10 years of data, we will be able to detect RRRs of 0.91 and 1.07 when comparing stages 0 to I. The RRRs we observed using 1 year data are actually much bigger than these, which indicate that we have adequate power.

Table 3. Detectable RRRs comparing other Stages to Stage I (assuming 80% power and 5% significance level)

	Category 1 versus Category 2	Category 3 versus Category 2
Stage 0 versus I	0.91	1.07
Stage II versus I	1.15	0.89
Stage III versus I	1.16	0.88
Stage IV versus I	1.29	0.80

We then calculate the detectable RRRs when we compare the transition outcome across the three groups for the first comparator. We again assume the distribution of the first comparator will be similar across 10 years and the transition probability for the reference category, "neither dissatisfied nor satisfied," was estimated from the 1 year transition in ADL stages for the three panels that were active in both 2005 and 2006. Relative risk of functional improvement is defined as the probability of ADL functional improvement divided by the probability of being stable in ADL stage. All the detectable risk ratios (Table 4) are smaller than 2 except for one RRR for institutionalization, which indicate ample power for our analysis.

Table 4. Detectable RRRs of transition (functional stable is the reference) for the three categories of the first comparator (assuming 80% power and 5% significance level)

	Death	Institutionalization	Functional deterioration	Functional improvement

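### Giving every non-significant coefficient zero points can put small ADL stage IV level with the reference while stage III scores, and the 'lowest' divisor is undefined for negative coefficients

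*Combined protocol and SAP*

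**What the plan says.** The Tool is built in three steps, described under Data Analysis after Aim 4. Candidates are screened by stakeholder and researcher judgement together with bivariable p < .20. Step 2 will "estimate a parsimonious model by using backward selection to remove all candidate variables at" p > .05. Step 3 divides each significant "coefficient by the lowest significant" one and rounds to an integer; a value of zero "will be assigned to non-significant" coefficients. A two-sided 5% level "will be used for all final tests of significance".

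The transition model behind the Tool has several equations: "The 5-state transition outcome will be modeled by multinomial logistic regression models with no change in function as reference". Each term therefore has four coefficients, for improvement, deterioration, institutionalization and death.

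Stage is a five-level factor that the Tool section lists among its adjusters. The only stage reference level stated is in Aim 2, which reports estimates "for the ADL and IADL stages (stage I as reference"); none is stated for the Tool. The access and quality comparators are coded as best and worst groups against the middle.

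Step 3 does not say how to score a non-significant level of a retained factor except by the zero rule. It does not say whether 'lowest' refers to value or magnitude, or which equation supplies the coefficients.

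**The concern.** After step 2, a variable that survives is significant in some sense. What is left for the zero rule to act on is mainly a single level of a multi-level factor, or a term's coefficient in one of the four outcome equations. Significance of a level depends on its size as well as its effect. Stage IV is the smallest ADL stage, so it can fail the 5% test when a larger, less disabled stage with an equal or smaller effect passes. The score would then place stage IV at the reference level and stage III above it.

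The divisor raises a second issue. Negative coefficients are likely under the plan's own coding: a 'best' comparator group against the middle and, if stage I is also the reference in the Tool, a stage 0 term. If 'lowest' is taken as most negative, every sign changes.

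The Tool is the project's final deliverable and is meant for use by outside health systems, so the point table has to follow unambiguously from the written rule.

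**Working it through.** **Group sizes.** Inputs are the raw ADL counts in Table 5: 8,208, 1,942, 995, 728 and 185, which sum to the stated 12,058. The fourth row carries a repeated stage II label; I read it as stage III. Scaling from 3 to 10 panels gives 12,058 × 10/3 = 40,193, within 0.5% of the stated 40,000. At 40,000:
- stage I: 40,000 × 1,942/12,058 = 6,442
- stage III: 40,000 × 728/12,058 = 2,415
- stage IV: 40,000 × 185/12,058 = 614

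**Chance that a stage level is non-significant.** The test is a two-sided 5% Wald test on ln(RRR), with stage I as reference. The variance is the sum of 1/(expected count) over four cells (event and no change, in each stage), multiplied by a design effect (deff). The probability of 0 points is 1 − Φ(ln RRR/SE − 1.96). Assumptions, none of them in the documents: 60% unchanged in stage I, stage I event rates of 1%, 2% and 5%, and deff of 1 or 2.

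Stage IV, RRR 2, rate 1%, deff 1:
- variance = 0.01552 + 0.00026 + 0.08229 + 0.00274 = 0.1008, so SE = 0.3175
- ln 2/0.3175 = 2.18; power = Φ(0.22) = 59%; chance of 0 points = 41%

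Stage III, same scenario:
- variance = 0.01552 + 0.00026 + 0.02091 + 0.00070 = 0.0374, so SE = 0.1934
- ln 2/0.1934 = 3.58; power = 95%; chance of 0 points = 5%

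Whatever the correlation between the two tests, the chance that stage III scores while stage IV gets 0 is at least 41% − 5% = 36% in this scenario.

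Chance that stage IV gets 0 points:

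| True RRR | deff | 1% | 2% | 5% |
|---|---|---|---|---|
| 1.5 | 1 | 80% | 65% | 33% |
| 2 | 1 | 41% | 14% | under 1% |
| 2 | 2 | 66% | 43% | 11% |
| 4 | 1 | about 0 | about 0 | about 0 |

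**A level that cannot be estimated.** Deterioration means moving to a higher stage. Someone at ADL-IV cannot do so, so the stage IV coefficient in the ADL deterioration equation is not estimable. Step 3 does not say how to score it.

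**Divisor.** Take assumed coefficients 0.60, 0.25, −0.15 and −0.40, all significant.
- Most negative as divisor (−0.40): −1.5, −0.625, 0.375, 1. Signs flip, and the significant −0.15 term rounds to 0.
- Smallest magnitude, signs kept (0.15): 4, 1.67, −1, −2.67, which rounds to +4, +2, −1, −3. No reversal.

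Table 3's RRRs of 0.91, 1.15, 1.16 and 1.29 for stages 0, II, III and IV, used only as illustrative effects, have logs −0.094, 0.140, 0.148 and 0.255. Dividing by −0.094 gives +1, −1, −2, −3; dividing by 0.094 gives −1, +1, +2, +3. If stage IV were non-significant, the zero rule would replace its +3 with 0, below stages II and III.

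**The case against.** Giving no points to a level whose effect is not established guards against scoring noise. The plan says it used this approach recently and cites published guidance, which cannot be checked here. Stakeholder input shapes the final variable list, counter-intuitive associations may be suppressed, and a final protocol and code are later deliverables. These are fair points. However, choosing variables does not settle how a level inside a retained factor is scored, and zero is itself an estimate: it says stage IV equals the reference.

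Several stronger readings are tempting, and the documents do not support them.
- *Any protective term reverses the ranking.* This requires 'lowest' to mean most negative. In a rule that divides by a unit and rounds, smallest magnitude is the workable reading, and with signs kept nothing reverses. A pure reversal would also be a visible mirror image; the lasting loss is coarser rounding.
- *One divisor is used across all four equations and the points are summed.* The text is silent. It refers to a set of Tools grouping people by expected outcome.
- *Stage IV is scored as no risk, or like stage 0.* Zero points means equal to the reference level, which is stage I where one is stated. Diagnoses, living circumstances and comparators still add points.
- *Table 4 fixes the institutionalization rate.* It gives detectable ratios only. Back-solving with a Wald test and the stage I comparator shares gives about 0.09% or 0.33% depending on the row at 40,000 people, and 0.29% or about 1.1% at 12,058.

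The problem also largely disappears for common outcomes or RRRs of 4 or more.

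**Conclusion.** The concern holds in a limited form. The zero rule is explicit and, followed as written, can misorder the levels of a retained factor. For ADL stage IV this is a material risk for rare outcomes with modest effects: about 41% at a 1% rate and RRR 2, or 66% with a design effect of 2. It is small at 5% (under 1%, or 11% with a design effect of 2). These figures rest on assumed event rates, an assumed share unchanged, stage I as reference, and no covariate adjustment or attrition. The documents supply only the stage counts and the significance level.

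The ambiguity of 'lowest' is a separate wording gap. It matters only if someone applies the most-negative reading, but the text does not rule that out. Both are worth correcting before the Tool is derived.

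**What to change.** Rewrite step 3 along these lines: test each multi-level factor jointly; when a factor is retained, give every level points from its own estimate, whether or not that level is individually significant; within each outcome equation, divide by the smallest absolute significant coefficient and keep the signs. Also name the Tool's reference level for stage, and state how the non-estimable ADL-IV deterioration coefficient is handled.

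This takes a few sentences and no new data. The cost is that some levels receive points from imprecise estimates, so confidence intervals should be shown beside the points. The Tool would also carry one score column per outcome.
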